7.6.2 Sensitivity Analysis

The MMRM is based on the assumption that missing data follow a MAR mechanism. A sensitivity analysis, based on the assumption that the missing data are MNAR, may be performed for the primary endpoint. The implementation of this analysis will depend on the extent and pattern of missing data and as such, it may not be used. For this sensitivity analysis, missing values will be imputed using jump to reference where it is assumed that following early discontinuation, the values for patients in the CBD group at future visits will follow the same distribution as the values of patients in the placebo group.

Each of the complete datasets will be analyzed using an Analysis of Covariance (ANCOVA) model which will model the change in total HQ-CT score from Baseline to Study Completion/Early Withdrawal and which will include fixed factors for treatment group and randomization strata of growth hormone treatment (yes, no), and baseline HQ-CT total score as a covariate. The results from the analyses of each complete dataset will then be combined using Rubin's method.

LS means and the LS mean difference between all CBD and placebo will be presented together with the relevant 95% CIs and p-values.

7.6.3 Multiplicity

Statistical inference for the primary endpoint and for the secondary endpoints [change in total body weight, responder rate, PGI-C, TFEQ-R18 (3 subscales), PROMIS[®] Life Satisfaction and Positive Affect (2 separate scores) and PROMIS[®] Physical Activity and Fatigue (2 separate scores)] will be controlled at an overall family wise error rate of $\alpha = 0.05$ using a gatekeeping approach. Using this

Statistical Analysis Plan

Sponsor Name: Insys Development Company, Inc.

Sponsor Protocol ID: INS011-16-085

Covance Study ID: 000000163564

approach, the hypotheses associated with the secondary endpoints will only be tested if the null hypothesis for the primary endpoint is rejected (i.e. if $p < 0.05$ for the primary endpoint).

In this instance, the 10 hypotheses corresponding to the secondary endpoints will be tested using the Hochberg procedure. The 10 p-values resulting from the inferential analyses of the secondary endpoints will be ordered from largest to smallest and will be compared with alpha critical values of $\alpha, \alpha/2, \alpha/3, \dots \alpha/(10-1)$. The largest p-value is then compared with α . If this p-value is not less than α , proceed to the second largest p-value and compared it with $\alpha/2$. Testing continues sequentially in this manner until a p-value for an endpoint is statistically significant. Once a p-value is statistically significant, conclude that the treatment effect for that endpoint and all endpoints with smaller p-values are statistically significant.

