8.6.3. Efficacy Analyses

Statistical inference for the primary endpoint and for key secondary endpoints will be controlled at an overall family wise error rate (alpha) of 0.05, 2-sided. For continuous endpoints, number of observations, mean, standard deviation (SD), median, minimum and maximum will be presented as descriptive statistics. For inferential statistics, analysis of covariance (ANCOVA) with the baseline value and randomization strata (growth hormone treatment) as covariates will be used. For multiple values, a repeated measures analysis will be performed. For categorical endpoints, the number of observations, frequency counts and percentages will be presented as descriptive statistics, and Fisher's exact test will be used for inferential statistics.

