7.1 General Principles

All data processing, summarization and analyses will be performed using Covance's SAS Environment / Version 9.4 (or later) of the SAS® statistical software package.

The analysis treatment group will be defined by the modal dose of study drug (dose of the study drug that the patient took for the longest period).

Statistical Analysis Plan

Sponsor Name: Insys Development Company, Inc.
Sponsor Protocol ID: INS011-16-085

Covance Study ID: 000000163564

The following principles will be applied to all TFLs unless otherwise stated:

Principle	Value
Significant tests	Two-sided and use a 5% significance level for main effects and 10% significance level for interaction terms
Treatment group labels and order presented	Listings: Placebo Cannabidiol Oral Solution (30 mg/kg/day) Cannabidiol Oral Solution (40 mg/kg/day) Tables: Placebo CBD (30 mg/kg/day) CBD (40 mg/kg/day) All CBD Total
Tables	Data in summary tables presented by treatment group and visit (where applicable)
Listings	All data collected presented by Treatment group Patient Visit (where applicable) Date; unless otherwise specified
Descriptive summary statistics for continuous variables	Number of patients/observations (n) Mean Standard deviation (SD) Median Minimum Maximum

COVANCE INC. CONFIDENTIAL

Document Date: 9 July 2018

Page 17 of 39
ST-AD-008 version 04

Downloaded by PPD on 10/12/2022

Statistical Analysis Plan

Sponsor Name: Insys Development Company, Inc.

Sponsor Protocol ID: INS011-16-085

Covance Study ID: 000000163564

Principle	Value
Descriptive summary statistics for categorical variables	Frequency counts and percentages [n (%)]
Denominator for percentages	Number of patients in the analysis population, unless stated otherwise in table shell(s)
Include "Missing" as category	Yes, when the number missing is greater than zero for at least one treatment group
Display for 0 percentages	Leave blank
Display to one more decimal place than collected value	Mean Mean Difference Median Percentages
Display to two more decimal places than collected value	Standard Deviation Confidence Interval
Limit of precision for displays	3 decimal places
Date Format	DDMMYYYY

Baseline is defined as the last scheduled or unscheduled measurement collected prior to first dose of double-blind investigational medicinal product (IMP) treatment.

Only data from scheduled post-baseline visits will be included in analyses and summary tables, all visit data will be listed.

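### SAP 7.6.3 lists Hochberg critical values only down to alpha/9 for ten secondary hypotheses, so the smallest p-value lacks its correct threshold of alpha/10

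*SAP*

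**What the plan says.** The protocol (8.6.3, Efficacy Analyses) requires inference on the primary and key secondary endpoints to be "controlled at an overall family wise error rate (alpha) of 0.05, 2-sided", and names no procedure.

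SAP 7.6.3 supplies one. Inference "will be controlled at an overall family wise error rate of $\alpha = 0.05$ using a gatekeeping approach": the secondary endpoints are tested only if the primary p-value is below 0.05. After that, "the 10 hypotheses corresponding to the secondary endpoints will be tested using the Hochberg procedure". The family is listed as "change in total body weight, responder rate, PGI-C, TFEQ-R18 (3 subscales") plus PROMIS "Life Satisfaction and Positive Affect (2 separate scores) and PROMIS[®] Physical Activity and Fatigue (2 separate scores"). "The 10 p-values resulting from the inferential analyses of the secondary endpoints will be ordered from largest to smallest" and are then "compared with alpha critical values of $\alpha, \alpha/2, \alpha/3, \dots \alpha/(10-1").

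The section goes on to compare the largest p-value with alpha and the second largest with alpha/2, and to continue on that pattern until one is significant. That endpoint and all those with smaller p-values are then declared significant. SAP 7.1 sets tests as "Two-sided and use a 5% significance level for main effects".

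**The concern.** The list starts at alpha for the largest p-value, so its denominator has to reach the number of hypotheses, which is ten. It stops at nine. The term left out is the strictest one, and it belongs to the smallest p-value. That is the step that decides the outcome when only one secondary endpoint shows a clear effect.

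This is the only decision rule for the secondary endpoints, and neither document gives alpha/10 anywhere else. A programmer has three options: test the smallest p-value at alpha/9, not test it at all, or infer alpha/10. The first can exceed the claimed error rate. The second discards a valid result. Only the third is Hochberg's procedure. Under the first, a smallest p-value between 0.0050 and 0.0056 would be declared significant when the named procedure says it is not.

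**Working it through.** **Inputs.** Alpha is 0.05, two-sided (protocol 8.6.3; SAP 7.1 and 7.6.3). The procedure is Hochberg with ten hypotheses (SAP 7.6.3). The documents give no correlations between endpoints, so those below are assumptions.

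**Number of hypotheses.** Weight 1 + responder rate 1 + PGI-C 1 + TFEQ-R18 3 + Life Satisfaction and Positive Affect 2 + Physical Activity and Fatigue 2 = 10. The SAP's count is right.

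**Thresholds.** The k-th largest p-value is compared with alpha/k.

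| k | Hochberg, m = 10 | SAP list |
|---|---|---|
| 1 | 0.0500 | 0.0500 |
| 2 | 0.0250 | 0.0250 |
| … | … | … |
| 9 | 0.05/9 = 0.00556 | 0.00556 |
| 10 | 0.05/10 = 0.00500 | not given |

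**The SAP's 0.05 under correct Hochberg.** Take all ten secondary nulls true, the gate open and p-values independent. Nearly all the error comes from the last step, so the family-wise error is close to 1 − (1 − c)^10, where c is the last threshold. With c = 0.0050 this gives 0.0489, and the exact calculation over all ten steps also gives 0.0489. The claim of 0.05 is met.

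**Reading A: smallest p-value tested at alpha/9.** With c = 0.05/9, 1 − (1 − 0.05/9)^10 = 0.0542, and the exact value is also 0.0542. The sum bound is 10 × 0.05/9 = 0.0556. The claim of 0.05 is not met.

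**Reading B: smallest p-value has no threshold.** The exact family-wise error is 0.0013. Nothing is inflated. However, if the smallest p-value is below 0.005 and the other nine miss their thresholds, Hochberg rejects and this rule cannot.

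**Effect of correlation.** Equicorrelated normal statistics, two-sided, 2,000,000 replicates per row, all ten nulls true, gate open:

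| Correlation | Last threshold alpha/9 | Last threshold alpha/10 |
|---|---|---|
| 0.1 | 0.0539 | 0.0487 |
| 0.2 | 0.0523 | 0.0473 |
| 0.3 | 0.0501 | 0.0453 |
| 0.5 | 0.0428 | 0.0390 |
| 0.7 | 0.0323 | 0.0294 |

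**Effect of the gate.** If the primary null is true, the gate alone holds the error at 0.05. At the design values in SAP 2.3 (30 per arm, difference 5, SD 6), the standard error is 6 × √(2/30) = 1.549, and 5/1.549 − 1.960 = 1.27, so power is 0.8975 by the normal approximation. If the primary and secondary tests were independent, reading A would give 0.8975 × 0.0542 = 0.0486. For a larger primary effect the gate opens almost surely and the figure returns to 0.0542.

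**Fewer than ten true nulls.** With nine or fewer true nulls, the listed thresholds are sufficient under the usual Hochberg conditions. In simulation with one false null (shift of 1 to 4 standard errors) and alpha/9 for the smallest p-value, the error is about 4.9% at correlation 0 and about 4.6% at 0.3.

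**The case against.** The other side accepts that the list is one term short and disputes how much follows.

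- **The intended rule can be recovered.** The section names Hochberg, says ten hypotheses, and gives the first two steps and the pattern. The tenth step on that pattern is alpha/10. This stands as evidence of a writing slip. But the last term is written out as a formula, (10−1), and could be programmed as written.
- **Inflation belongs to one reading only.** Strictly, alpha/9 is the ninth value, so it belongs to the second-smallest p-value, and the smallest has none. This stands. That reading is conservative, but it is also not Hochberg.
- **The harmful configuration is unlikely.** It needs all ten secondary nulls true and the gate open almost surely. One secondary is a responder rate built on the same HQ-CT score as the primary (SAP 7.6.4.2), so an effect that opens the gate would ordinarily make that null false, and control then holds. This largely stands. Exceptions exist, for example a mean shift that leaves the responder proportion unchanged, or dropout counted as non-response that offsets a benefit. So control is made likely but is not proved.
- **5.42% treats every p-value as uniform.** The responder rate uses Fisher's exact test, which is conservative. With 33 per arm and assumed common response rates of 10% to 40%, it rejects at 0.05/9 with probability about 0.0009 to 0.0025. Then 1 − (1 − 0.05/9)^9 × (1 − 0.0025) = 0.051 at the top of that range, and about 0.050 at the bottom. This stands and narrows the excess.
- **Endpoints from the same patients are correlated.** This is plausible, and above about 0.3 the error is below 0.05 even with alpha/9. But the SAP claims control without that condition and gives no correlations.

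These points reduce the size. None of them supplies the missing threshold.

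**Conclusion.** The concern holds. The critical values in SAP 7.6.3 are wrong as written: the sequence ends at 0.00556 where the tenth step of the named procedure requires 0.0050. On either literal reading the rule is not Hochberg's, and on reading A control at 0.05 is not guaranteed.

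The numerical effect is small. The excess is 0.42 percentage points with ten independent, exactly uniform p-values, at most 0.56 points by the sum bound, and about 0.1 points or less once the conservatism of Fisher's test is allowed for. It vanishes at moderate correlation. These figures assume that all ten secondary nulls are true and the gate is open. A decision changes under reading A only if the nine larger p-values miss their thresholds and the smallest lies between 0.0050 and 0.0056. Under reading B it changes whenever the smallest is below 0.0050 and the other nine miss theirs.

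It should still be corrected, because it is a definite error in the prespecified inferential rule for every secondary endpoint.

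**What to change.** In SAP 7.6.3, replace the list with alpha, alpha/2, alpha/3, …, alpha/10, and add that the k-th largest p-value is compared with alpha/k for k = 1 to 10, so that the smallest is tested at 0.0050. With that sequence the family-wise error is 0.0489 for independent tests with all ten nulls true, within the claimed 0.05.

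The cost is one line of SAP text, with no effect on sample size, data collection or the primary analysis. It should be done before unblinding. Afterwards, the same correction could look data-driven if the smallest p-value fell between 0.0050 and 0.0056.

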7.6.4 Secondary Efficacy Analysis

The analyses of the secondary efficacy endpoints will be based on the placebo and all CBD treatment groups in the ITT population. Descriptive statistics for the secondary efficacy endpoints will be based on all treatment groups, i.e. placebo, CBD (30 mg/kg/day), CBD (40 mg/kg/day), all CBD and total.

Listings of secondary efficacy endpoint data will be produced for the ITT population.

7.6.4.1 Change in Total Body Weight

Change from Baseline to Study Completion/Early Withdrawal in body weight will be analyzed using the MMRM method described for the primary efficacy endpoint. The MMRM model will include change in total body weight at each scheduled visit, fixed factors for treatment group, time (study week), randomization strata of growth hormone treatment (yes, no), a treatment-by-time interaction term, and baseline total body weight as a covariate.

LS means and the LS mean difference between all CBD and placebo will be presented together with the relevant 95% CIs and p-values. In addition, LS means and the 95% CIs will be plotted by treatment group and visit.

7.6.4.2 Responder Rate

A responder is defined as a 6-point decrease in HQ-CT total score from Baseline to Study Completion/Early Withdrawal. The responder rate data will be analyzed using Fisher's exact test and patients with missing HQ-CT score at Study Completion/Early Withdrawal will be treated as non-responders.

The proportion of responders and non-responders will be presented by treatment group, together with the difference in proportion, its associated 95% CI and the

Statistical Analysis Plan

Sponsor Name: Insys Development Company, Inc.
Sponsor Protocol ID: INS011-16-085

Covance Study ID: 000000163564

comparison p-value from the Fishers exact test. The proportion of responders will be plotted by treatment group and visit.

7.6.4.3 PGI-C

PGI-C will be analyzed using the MMRM method described for the primary efficacy endpoint, which will include PGI-C at each scheduled visit, fixed factors for treatment group, time (study week), randomization strata of growth hormone treatment (yes, no), a treatment-by-time interaction term, and PGI-S score at baseline as a covariate.

LS means, the LS mean difference between all CBD and placebo, as well as the relevant 95% CIs and p-values will be presented. A plot of the LS means and their associated 95% CIs by treatment group and visit will be produced.

7.6.4.4 Change TFEQ-R18

Change from Baseline to Study Completion/Early Withdrawal in each TFEQ-R18 subscale will be analyzed using the MMRM method described for the primary efficacy endpoint. For each subscale, the MMRM model will include change in TFEQ-R18 subscale score at each scheduled visit, fixed factors for treatment group, time (study week), randomization strata of growth hormone treatment (yes, no), a treatment-by-time interaction term, and baseline TFEQ-R18 subscale score as a covariate.

LS means and the LS mean difference between all CBD and placebo will be presented together with the relevant 95% CIs and p-values. In addition, LS means and the 95% CIs will be plotted by treatment group and visit.

7.6.4.5 Change in Quality of Life

Quality of life will be assessed using the PROMIS[®] Life Satisfaction and Positive Affect short-form questionnaires. Change in PROMIS[®] Life Satisfaction from Baseline to Study Completion/Early Withdrawal and change in PROMIS[®] Positive Affect from Baseline to Study Completion/Early Withdrawal will be analyzed separately using the MMRM described for the analysis of the primary endpoint.

The MMRM analysis described for the primary endpoint will be used to analyze the change in PROMIS[®] score (Life Satisfaction or Positive Affect) from Baseline to Study Completion/Early Withdrawal. For each analysis, change in PROMIS[®] score (Life Satisfaction or Positive Affect) at each visit will be included in the model, together with fixed factors for treatment group, time (study week), randomization strata of growth hormone treatment (yes, no), a treatment-by-time interaction

Statistical Analysis Plan

Sponsor Name: Insys Development Company, Inc.

Sponsor Protocol ID: INS011-16-085

Covance Study ID: 000000163564

term, and baseline PROMIS[®] score (Life Satisfaction or Positive Affect) as a covariate.

The resulting LS means, LS mean difference between all CBD and placebo, 95% CIs and corresponding p-values will be presented. LS means and the 95% CIs will be plotted by treatment group and visit.

7.6.4.6 Change in Physical Activity

Physical Activity will be assessed using the PROMIS[®] Physical Activity and Fatigue questionnaires. Change in PROMIS[®] Physical Activity from Baseline to Study Completion/Early Withdrawal and change in PROMIS[®] Fatigue from Baseline to Study Completion/Early Withdrawal will be analyzed separately using the MMRM described for the analysis of the primary endpoint.

For each analysis, change in PROMIS[®] score (Physical Activity or Fatigue) from Baseline to Study Completion/Early Withdrawal, the MMRM model will include change in PROMIS[®] score (Physical Activity or Fatigue) at each scheduled visit, fixed factors for treatment group, time (study week), randomization strata of growth hormone treatment (yes, no), a treatment-by-time interaction term, and baseline PROMIS[®] score (Physical Activity or Fatigue) as a covariate.

LS means and the LS mean difference between all CBD and placebo will be presented together with the relevant 95% CIs and the comparison p-value. In addition, LS means and the 95% CIs will be plotted by treatment group and visit.

7.6.5 Subgroup Analysis

Not applicable.

7.6.6 Exploratory Efficacy Analysis

The exploratory efficacy analysis will be based on the DEXA population. Total fat, fat free mass, bone mineral content and lean body mass, together with changes from baseline will be summarized by treatment group and visit using standard descriptive statistics.

All DEXA scan data will be listed.

7.6.7 Columbia Suicide Severity Rating Scale

Responses Columbia Suicide Severity Rating Scale (C-SSRS) will be listed separately for the adult and child-completed assessments. The listings will be based on the ITT population.

Statistical Analysis Plan

Sponsor Name: Insys Development Company, Inc.
Sponsor Protocol ID: INS011-16-085

Covance Study ID: 000000163564

7.7 Safety

7.7.1 Extent of Exposure

Duration of exposure will be defined in days as:

$$(\text{date of last dose} - \text{date of first dose}) + 1.$$

Duration of exposure will be summarized using descriptive statistics for each treatment group for the Safety population.

7.7.2 Adverse Events

All AEs recorded on the eCRF will be coded using the MedDRA dictionary [Version 21.0 (or a later version if updated during the study)] and classified as treatment – emergent AEs (TEAEs) as follows:

- TEAEs are events with start date on or after the date of first dose of double-blind IMP and up to 14 days after the last dose of double blind IMP or events with start date prior to the date of first dose of double-blind IMP whose severity worsens on or after the date of first dose of double-blind IMP.

All AE data will be listed by treatment group. Treatment-emergence status will be flagged in the listing. In addition, corresponding listings of treatment-emergent serious AEs (TESAEs), AEs leading to permanent discontinuation of IMP and AEs resulting in death will be produced.

Summary tables of TEAEs by treatment group and overall will be produced for the Safety population. No statistical comparisons of AEs between treatment groups will be performed.

The severity of all AEs is recorded as mild, moderate, or severe. If severity is missing for a TEAE, it will be considered severe.

The relationship between an AE and IMP treatment is assessed as definite, probable, possible, unlikely or not related. A treatment-related AE is an AE considered by the investigator as definitely, possibly, or probably related to IMP treatment or with unknown/missing relationship to IMP treatment.

An overview table will summarize the number and percentage of patients with at least one of the following TEAEs, where patients with more than one TEAE in a particular category are counted only once in that category:

- any TEAE;
- TEAE by severity (mild, moderate, severe);
- treatment-related TEAE;
- severe treatment-related TEAE;

COVANCE INC. CONFIDENTIAL

Document Date: 9 July 2018

Page 26 of 39
ST-AD-008 version 04

Downloaded by PPD on 10/12/2022

Statistical Analysis Plan

Sponsor Name: Insys Development Company, Inc.

Sponsor Protocol ID: INS011-16-085

Covance Study ID: 000000163564

- TESAE;
- TESAE by severity;
- treatment-related TESAE;
- TEAE leading to study drug discontinuation.

The overview table will be repeated to summarize the number of TEAEs (displaying the number and percentage of observed events).

The number and percentage of patients reporting each AE will be summarized by System Organ Class (SOC) and Preferred Term (PT) for the Safety population. Tables will be sorted alphabetically by SOC. PTs will be sorted by descending overall total. The following summaries will be produced:

- AEs occurring in the run-in period, by SOC and PT;
- TEAEs, by SOC and PT;
- TEAEs related to IMP treatment, by SOC and PT;
- TEAEs by relationship to IMP treatment, by SOC and PT;
- TEAEs by maximum severity, by SOC and PT;
- TEAEs related to IMP treatment by maximum severity, by SOC and PT;
- TEAEs causing discontinuation from IMP treatment, by SOC and PT;
- TEAEs related to IMP treatment causing discontinuation from IMP treatment, by SOC and PT;
- TESAEs, by SOC and PT;
- TESAEs related to IMP treatment, by SOC and PT;
- TEAEs leading to death, by SOC and PT.

In the above summaries, patients with more than one TEAE within a particular SOC are counted only once for that SOC. Similarly, patients with more than one TEAE within a particular PT are counted only once for that PT. For summaries by maximum severity, patients with multiple TEAEs within a particular SOC or PT will be counted under the category of their most severe TEAE within that SOC or PT. TEAEs with missing intensity/severity will be included (as severe) in the overall count of patients with TEAEs, but will not be included in the counts of patients with TEAEs within a SOC or PT.

COVANCE INC. CONFIDENTIAL

Document Date: 9 July 2018

Page 27 of 39
ST-AD-008 version 04

Downloaded by PPD on 10/12/2022

Statistical Analysis Plan

Sponsor Name: Insys Development Company, Inc.
Sponsor Protocol ID: INS011-16-085

Covance Study ID: 000000163564

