4.3. Method of Assigning Patients to Treatment Groups

Following the 2-week Placebo Lead-In Period of the study, patients will be randomized in a 1:1 ratio, using a web-based randomization system. The randomization will be stratified according to growth hormone treatment (yes/no).

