4.6. Treatment Compliance

The prescribed dosage, timing, and mode of administration of Cannabidiol Oral Solution may not be changed unless a safety concern or toxicity is identified for a patient.

Patient compliance will be calculated during Placebo Lead-In Period. Patients taking too much or too little study medication should be re-educated on the proper use of study medication. Non-compliance (<80% or >100%) should be evaluated by the Investigator for the need to withdraw the patient. The Investigator should discuss the case with the Medical Monitor.

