8.5. Analysis Populations

Statistical analysis will be done on the following populations:

- **Intent to Treat (ITT) Population:** The ITT Population will include all patients who were randomized. The ITT Population will be used for all efficacy analyses.
- **Safety Population:** The Safety Population will include all patients who were treated with at least one dose of the study drug. The Safety Population will be used for all safety assessments.

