3.4 Safety Endpoints

The safety endpoints of this study are:

- Treatment-emergent adverse events (TEAEs)
- Clinical laboratory assessments
- Vital signs (blood pressure, pulse rate, respiration rate and temperature)
- 12-lead ECGs
- Physical examination assessments
- Pregnancy screens
- Urine drug screen (including THC)
- Medical history
- Prior and concomitant medications.

4. Pharmacokinetic Endpoints

The pharmacokinetic (PK) endpoints of this study are trough concentrations (C_{trough}) of cannabidiol (CBD) and metabolite 7-OH-CBD which will be used to assess the exposure-response relationship.

Statistical Analysis Plan

Sponsor Name: Insys Development Company, Inc.
Sponsor Protocol ID: INS011-16-085

Covance Study ID: 000000163564

5. Analysis Populations

Unless otherwise stated, all efficacy analyses will be performed on the Intent-to-treat (ITT) population. A supportive analysis of the primary endpoint will also be performed on the Per-protocol (PP) population. All safety analyses will be performed on the safety population. Analyses of the DEXA endpoints will be performed on the DEXA population. The analysis of the PK endpoints will be performed on the PK population.

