5.2 Safety Population

The Safety population includes all randomized patients treated with at least one dose of the study drug during the double-blind treatment period. Safety patients are analyzed according to their actual treatment received.

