7.2 Subject Disposition and Data Sets Analyzed

Patient disposition will be listed and summarized by treatment group and overall and will include the number and percentage of patients:

- screened;
- entered placebo lead-in period;
- screened and not randomized;
- randomized (i.e. entered the titration period);
- randomized and not treated with double-blind treatment;
- treated with double-blind treatment;
- entered the maintenance period;
- entered the taper period;

COVANCE INC. CONFIDENTIAL

Document Date: 9 July 2018

Page 18 of 39
ST-AD-008 version 04

Downloaded by PPD on 10/12/2022

Statistical Analysis Plan

Sponsor Name: Insys Development Company, Inc.

Sponsor Protocol ID: INS011-16-085

Covance Study ID: 000000163564

- continued to the long-term safety study;
- included in each study population (Safety, ITT, PP, DEXA, PK).

In addition, the number and percentage of patients who complete the study and who discontinue early, including a breakdown of the primary reasons for discontinuation from the study will be presented.

A summary of patient randomization by site will also be provided by treatment group and overall for the ITT population. Inclusion/exclusion criteria not met will be listed for all screened patients.

In addition, a summary table and listing will be produced for discrepancies between the stratification factors in the database and IWRS. This will be produced for the ITT population.

A listing of study drug kit numbers and assignments will be produced.

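### The run-in adverse event table is built on the Safety population, so it leaves out every child who took lead-in placebo but was not randomised and dosed double-blind

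*SAP*

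**What the plan says.** SAP 7.7.2 introduces its list of adverse event tables with the rule "The number and percentage of patients reporting each AE will be summarized by System Organ Class (SOC) and Preferred Term (PT) for the Safety population". The first table in that list is "AEs occurring in the run-in period, by SOC and PT". SAP Section 5 makes the same rule general: "All safety analyses will be performed on the safety population". SAP 5.2 defines the set: "The Safety population includes all randomized patients treated with at least one dose of the study drug during the double-blind treatment period".

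The lead-in comes before randomisation. Protocol 4.3 states: "Following the 2-week Placebo Lead-In Period of the study, patients will be randomized in a 1:1 ratio, using a web-based randomization system". Lead-in patients receive matching placebo for two weeks (Protocol 4.1.2), and adverse events are reviewed at every visit from Screening (Protocol Table 1).

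The plan expects some children to stop before randomisation. Patients may leave at any time (Protocol 3.3 and 3.4), and Protocol 4.6, on compliance in the lead-in, says: "Non-compliance (<80% or >100%) should be evaluated by the Investigator for the need to withdraw the patient". The disposition table in SAP 7.2 has a line for patients who "entered placebo lead-in period" and further lines for those screened but not randomised and for those randomised but not treated double-blind.

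**The concern.** A run-in table would be expected to describe everyone who entered the run-in. This one describes only those who got through it and then took double-blind medication. A child who stopped lead-in placebo because of an adverse event is in neither the numerator nor the denominator.

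What is at stake is complete safety reporting in a paediatric trial. The study report would show how many children entered the lead-in and how many were randomised, but no summary of what happened to the difference. A reader of the run-in table could take it as the experience of all children on lead-in placebo, which it is not. The matter is descriptive: no planned test or comparison uses this table.

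**Working it through.** The main check is one of set membership.

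1. **Who is in the table.** Safety population = randomised AND at least one double-blind dose (SAP 5.2).
2. **Who took lead-in placebo.** Everyone dosed from Visit 2 (Protocol 7.2.1 and Table 1).
3. **Who is lost.** Left during the lead-in implies not randomised (Protocol 4.3 and 7.3.1), so the overlap with the Safety population is empty. Children who finished the lead-in but were not randomised, and any randomised but never dosed double-blind, are lost too. Coverage of all these children is 0%, whatever their number.
4. **Is there an exception?** None was found. SAP Section 5 defines the ITT, Safety, PP, DEXA and PK populations. None is a lead-in set, and SAP 7.7.2 does not exempt the run-in table.

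**Do other outputs recover the events?**

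| Output | Rule in the plan | Child never dosed double-blind |
|---|---|---|
| Serious event, discontinuation and death tables (SAP 7.7.2) | Treatment-emergent only, counted from the first double-blind dose | Excluded |
| Medical history summary (SAP 7.4.2) | ITT population | Excluded if never randomised |
| Listing of all adverse event data (SAP 7.7.2) | No population named; arranged by treatment group | Possible, but no group is stated |
| Listings of events leading to discontinuation or death (SAP 7.7.2) | Not limited to treatment-emergent events | Possible, but no group is stated |
| Disposition (SAP 7.2) | Counts and reasons for discontinuation | Counted; events not described |

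The listing groups in SAP 7.1 are placebo, 30 mg/kg/day and 40 mg/kg/day. The medical history row matters because Protocol 6.2.6.1 sends events reported before dose administration to medical history without saying whether the lead-in or the double-blind dose is meant.

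**How many children?** The documents give no lead-in attrition, so this is an illustration under an assumed loss d. With about 66 randomised (SAP 2.2), number entering = 66/(1 − d), rounded up:

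- d = 5%: 66/0.95 = 69.5, so 70 enter and 4 are left out.
- d = 10%: 66/0.90 = 73.3, so 74 enter and 8 are left out.
- d = 20%: 66/0.80 = 82.5, so 83 enter and 17 are left out.

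**Which way would the table be off?** Suppose 10% of randomised and dosed children had a run-in event, so the table shows 10%. Let p be the share among those left out. The share among all who entered is 0.10(1 − d) + p·d.

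| Assumed p | d = 5% | d = 10% | d = 20% |
|---|---|---|---|
| 50% (most leave because of events) | 12% | 14% | 18% |
| 5% (shorter exposure, other reasons for leaving) | 9.75% | 9.5% | 9.0% |

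Both values of p are assumptions. The sign changes between them, so the documents do not fix the direction.

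**The case against.** The best defence has four parts.

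- **The events are not lost to reporting.** SAP 7.7.2 lists all adverse event data without naming a population, and Protocol 8.6.4.1 promises patient listings of adverse and serious adverse events. Serious events are captured from consent (Protocol 6.2.6.4) and go to the sponsor within 24 hours (Protocol 6.2.6.7). This stands. A reader might infer from the table rule that every such event disappears, and the documents do not support that. What remains is the absence of a summary and of a stated place in the listing.
- **Bias is not shown.** A reader might infer that the table understates the run-in event rate, since leavers could be those with events. The objection to this also stands: the one withdrawal trigger specific to the lead-in is compliance, and the sign depends on unsupported inputs.
- **The table is an extra.** Protocol 8.6.4.1 confines adverse event summaries to treatment-emergent events. That is true, but the SAP commits to a run-in table, and its population should match its title.
- **One denominator is useful.** Keeping the Safety population lets the same children be compared before and after randomised dosing, and never-randomised children have no arm. This is a fair reason to keep that view, but not a reason to omit the others, since separate columns can show both.

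The protocol's own definition (8.5) is looser: "The Safety Population will include all patients who were treated with at least one dose of the study drug". It could be read to include lead-in placebo. It does not rescue the table, because the SAP uses its own narrower definition. The difference between the two is a separate matter.

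**Conclusion.** The point holds as a minor one. The run-in table is incomplete by construction: it covers no child who took lead-in placebo without going on to randomised double-blind dosing, and serious events in these children reach no summary table. This follows from the definitions alone and needs no numerical assumption.

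How many children and events are affected is unknown. The counts of 4, 8 and 17 rest on assumed lead-in losses and about 66 randomised. Neither the size nor the direction of any distortion can be derived from the documents. The comparison of treatment-emergent events between arms, the primary analysis and the power are not affected.

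**What to change.** - In SAP Section 5, define a lead-in set: all patients who took at least one dose of lead-in placebo.
- In SAP 7.7.2, base the run-in table on that set and identify serious events. Give it three columns: later randomised and dosed double-blind (the current Safety population view, by arm if wanted), not randomised or not dosed, and total.
- Add a non-randomised group to the adverse event listing.
- State that events between the first lead-in dose and the first double-blind dose count as adverse events and not as medical history, so that the table has the data it needs.
- Keep the Safety population for the treatment-emergent tables.

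The cost is one extra analysis set, its count in the disposition table, and a slightly larger run-in table. Adverse events are already reviewed from Screening, so no new assessment is needed. The present view is kept as one of the columns.
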